The effects of Remote Microphone Hearing Aids (RMHAs) on classroom listening, listening-in-noise and attention skills in children, aged 7-12, with Auditory Processing Disorder (APD)

(Student Study)

NCT02353091

26/03/20

The research was funded as a PhD studentship by GN Resound (Company sponsor), which also provides the FM systems that will be used in this study, and a UCL Impact award.

Summary

Children with Auditory Processing Disorder (APD) have poor auditory processing skills in the presence of normal peripheral hearing. These children are found to have worse listening-in-noise skills than typically developing peers, while other commonly reported symptoms include poor attention and distractibility. One of the management strategies for children with APD is the use of Remote Microphone Hearing Aids (RMHAs), which can help improve the signal-to-noise ratio in the child's ears. The aim of this randomised control trial was to examine whether RMHA use improves classroom listening for children with APD, and to further test their effects on children's listening-in-noise and attention skills following a 6-month intervention.

The principal research question is whether RMHAs improve classroom listening, listening in noise performance, listening in spatialised noise and auditory attention, in children with Auditory Processing Disorder (APD). We hypothesize that RMHA use will lead to improved classroom listening and improved speech-in-noise skills after 6 months of RMHA use. Additionally, we hypothesise that listening in spatialised noise and attention skills will remain unchanged following the intervention period.

Twenty-six (26) children with a diagnosis of an APD from the Great Ormond Street Hospital Audiology clinic will be recruited. The children need to fulfil the following criteria:

1. Diagnosis of APD based on routine clinical tests, administered by qualified audiologists, and requiring the following conditions:
2. No neurological or pervasive disorder or developmental delay. Children with a diagnosis of Attention Deficit Hyperactivity Disorder, epilepsy, Autism Spectrum Disorder, Developmental Language Disorder, Down Syndrome were excluded from the study.
3. Non-verbal cognitive ability score (IQ) of 85 or more.
4. Aged between 7-12 years.
5. Native English speakers.
6. No prior use of RMHAs.

Background and justification of the study

Auditory Processing Disorder

Auditory Processing Disorder (APD) is a disorder where the functions of the ear (outer, middle, inner) are normal but the person has difficulty identifying or discriminating sounds (1). For children with APD it is particularly difficult to hear when the listening conditions are not ideal. For example, when there is background noise it becomes really challenging to focus on the speaker. Two other factors that influence their hearing ability are reverberation and the distance

from the speaker (2). Some of the most commonly reported symptoms in these children are difficulties listening in background noise and inattentiveness, also reflected in findings from behavioural tests (3,4). Children with APD perform worse in behavioural tests measuring Speech-in-Noise (SiN) skills compared to typically developing children (5,6) and have worse performance in sustained auditory attention compared to children suspected of APD but not meeting APD diagnostic criteria (7).

Remote Microphone Hearing Aids

One of the management strategies recommended to children with APD is the use of Remote Microphone Hearing Aids (RMHAs). These are wireless listening devices that pick up the speaker's voice and transmit it to a receiver in the listener's ear. The use of this system helps improve the signal-to-noise ratio for children and bypasses the negative effects of background noise and reverberation in the classroom (8,9,2). However, only a handful of studies examined the effects of RMHA use on children with APD on specific measures (i.e. SiN, listening in noise, language and communication, and memory skills) (9–12).

Previous research suggests that children with APD after a prolonged use of RMHAs benefit from improved speech perception which is possibly linked to an enhanced auditory system (9). Adding to that, children with APD have shown improved speech in noise perception when using the RMHA, hence emphasizing the advantages of the device in discriminating speech in background noise (9,12).

Attention and ability to listen in spatialised noise in children with APD after the use of an FM system has been looked at by one uncontrolled study (12). As the central point of this study will be the use of the RMHA by children with APD for 6 months, it is expected that the findings could add valuable information on the subject. In addition, possible benefits of the system will be examined in detail. More particularly, possible long-term improvements in speech in noise performance (unaided), listening in spatialised noise (unaided), and auditory attention (unaided) will be examined.

Listening in noise and attention

A study compared the scores in the Hearing in Noise test of 10 children with APD at baseline unaided and after 5 months of daily RMHA use at school (9). The use of RMHAs during the aided test condition at 5 months gave a gain of approximately 10 dB in the SiN test compared to the unaided testing at baseline, with the authors concluding that RMHA use improved the auditory system in children with APD (9). However, this SiN improvement in the aided condition may reflect an auditory acclimatisation benefit similar to the one reported for hearing aids (13), as there was no significant improvement between pre- and post-intervention in unaided SiN testing. Another APD study used low-gain hearing aids equipped with a directional microphone and noise reduction (14), to examine changes in aided SiN skills in 14

children with APD. They reported improved aided SiN test results¹ after 6 months of RMHA use. Another intervention trial examined the ability to listen in spatial noise² on 28 children with APD who used RMHAs for 5 months (12). Children were tested on two tasks, easy words and hard words, and two conditions, with and without the RMHA at baseline and post-intervention. Results showed a significant improvement only in the easy words task when comparing the unaided with the aided conditions (12). All three trials lacked control groups and randomised designs, thus further validation in controlled trials, especially in unaided conditions, is required.

Furthermore, to date only one study looked into the long-term impact of RMHAs on behavioural attention tests in children with APD. Specifically, sustained auditory and sustained visual attention was examined in 28 children with APD after a 5-month RMHA intervention, without showing any significant change over the intervention period (12). One other study used the Children's Auditory Performance Scale questionnaire, completed by parents at baseline and after 6 months of using the directional microphone hearing aids at school (14). While the Auditory Attention Span subscale of the questionnaire showed significantly improved scores post-intervention, it still remained below what was considered normal cut-off. Parents observed their children at home, when hearing aids were not used, suggesting that the improvement in the subscale scores may have been due to lasting effects on their attentive behaviours. The findings from these two studies are conflicting, but none of the trials used a randomised control design (14).

Aim and hypotheses

In the present study we aim to test the impact of long-term RMHA use on self-reported listening, behavioural SiN performance and to assess behaviourally whether listening-in-spatialised-noise skills change after prolonged RMHA use and to assess the impact RMHA use has on attention skills.

Research questions:

The principal research question was to examine the effects of RMHAs on classroom listening, listening in noise performance, and auditory attention in children with APD.

Hypotheses:

- i. Children with APD who use RMHAs will show greater improvements in classroom listening, listening in noise and sustained auditory attention (unaided) after 6 months of RMHA use in comparison to the APD control group.

¹ The North Western University word-list was used in combination with speech-shaped noise coming from 180° that was individually adjusted (14).

² Words from the Lexical Neighbourhood Test were presented from the front, while a 100-talker babble recording was presented left, right, and behind the subject (12).

- ii. Children with APD who use the RMHA will not show greater improvements in listening in spatialised speech noise and divided and visual attention measures after 6 months of RMHA use in comparison to the APD control group.

Summary of main issues

Research suggests that children with APD after a prolonged use of RMHAs benefit from improved speech perception which is possibly linked to an enhanced auditory system (9). Adding to that, children with APD have shown improved speech in noise perception when using RMHAs (in an uncontrolled study); hence emphasizing the advantages of RMHAs in discriminating speech in background noise (9). There are not many studies, though, that focus on the use of RMHAs on children with APD.

This study will assess the effects of RMHA use on a range of outcome measures. As the central point of this study will be the use of RMHAs by children with APD for 6 months, it is expected that the findings could add valuable information on the matter. In addition, possible benefits of RMHAs will be examined in detail. More particularly, possible improvements in auditory attention, listening in spatialised noise and speech in noise discrimination (unaided) will be looked into.

Intervention ethical issues:

We will split the children with APD into (a) children who will only receive the RMHA, (b) children who will not receive any intervention for the study period (this group will receive the RMHA after we complete the study, at 6 months under this conditions: The recommendations by the APD clinic at GOSH include RMHA use as management strategies.

Currently from an audit conducted at GOSH APD Clinic, only 1 in 3 children who are recommended to have a RMHA obtain this by school funding (or by their parents funding the device) and this takes place several months after the recommendation has been made. Therefore, provision of this device is not standard practice. As such RMHAs are issued as part of this research study under the condition mentioned above.

An inclusion of a control, no intervention group, is essential for the Randomised Control Trial design we follow.

School and teacher involvement:

The teachers of the children who receive the FM systems will be provided with an information sheet and consent form and will be required to wear the microphone (which picks up the teacher's voice and transmits it wirelessly to the ear receivers in the child's ear) for the duration of the class. Remote microphone hearing aids are provided (funded by the school budget) to some children after clinical recommendations and this is not an unusual situation within the school environment.

We will liaise with the teacher as well as the Special Educational Needs Co-ordinator (SENCO) of the school in order to ensure that the school will be aware that the student has been issued with the RMHA. A general guide for the system will be made available in addition to information conveyed by the Research Fellow (PhD student) who will visit the school once per term.

Informed consent:

The child's parents will be given detailed written information and consent forms to sign about taking part in the study. They will be given up to a week to study and decide whether they wish for their child to participate in the study. They will only be allowed to take part once they have understood the purpose and procedures of the study and they have signed the consent forms. In addition, children will also be given information sheets adjusted to their age. Written assent from the children in the presence of their parents or carers will be sought.

Rights to withdraw from the study:

This will be outlined on both the information sheet and consent form and explained verbally throughout. This information will state that participants will be allowed to withdraw from the study at any point should they wish to do so. Withdrawal from the study will not involve any penalty or loss of benefit to them –this information is clearly underlined at the information sheet and will be made clear to them verbally.

Data protection:

The parents of the participant and the participant will be informed that their information will be anonymised and kept confidential. Data will be anonymised prior to analysis by the use of participant codes. Storage of the data will be within a secure password protected database and locked filing unit within UCL, in accordance with the data protection act 1998. If withdrawals take place the participants' data will be deleted.

Research Design and Methodology

Participants and Recruitment

We will recruit 26 children, 7-12 years old. All children will have been diagnosed and referred from the Auditory Processing Disorders Clinic at Great Ormond Street Hospital. The total sample size is decided using this power sample: $N = 24$ (total sample size) calculated using the F test for repeated measures between-within interaction Analysis of Variance (ANOVA) based on an estimated 0.5 effect size $f(U)$, 80% power, at 5% significance, using 2 groups and 3 measurement points. To account for a 10% loss due to follow-up, the total sample size of this study was 26 children, aged 7-12.

Inclusion criteria:

1. Diagnosis of APD based on routine clinical tests, administered by qualified audiologists, and requiring the following conditions:

- a) Reported parental SiN and other reported listening difficulties.
 - b) Normal peripheral hearing and middle ear function; i.e. air conduction PTA below 20 dB in all octave frequencies between 250 Hz and 8 KHz (31), middle-ear pressure between -150 to +50 daPa, middle-ear admittance between 0.3 to 1.6 cm³ and ear-canal volumes between 0.4 to 1.0 cm³ (32).
 - c) Abnormal performance on the Auditory Figure Ground (AFG) SiN test of the SCAN-3 C (i.e. at the 1st percentile score as per UK norms), and
 - d) Abnormal performance (-2 SDs from the normative mean) on at least one auditory processing test (i.e. Frequency Pattern Test [FPT], Dichotic Digits Test [DDT], duration pattern test, Gaps-in-Noise [GiN] or random gap detection pattern tests), or a score of -3 SDs from the normative mean on only one auditory processing test (any test from conditions 'c' and 'd'), and/ or abnormal performance (-2 SDs from the mean) on the Spatial Advantage and Total Advantage/ High-cue Speech Reception Threshold (SRT) subtests of the Listening in Spatialised Noise – Sentences (LiSN-S) test.
2. No neurological or pervasive disorder or developmental delay. Children with a diagnosis of Attention Deficit Hyperactivity Disorder, epilepsy, Autism Spectrum Disorder, Developmental Language Disorder, Down Syndrome were excluded from the study.
 3. Non-verbal cognitive ability score (IQ) of 85 or more.
 4. Aged between 7-12 years.
 5. Native English speakers.
 6. No prior use of RMHAs.

Subjects will be semi-randomly assigned to each of two intervention arms. The two groups will be stratified for age and balanced for sex.

Children will be given RMHAs to use at school and will be compared to the control (no intervention) group. Children will be enrolled in the study for 6 months. All groups will be tested before the start of the RMHA intervention, after 3 months, and at the end of the study (after 6 months of use of the interventions).

Following are the assessments to be performed for both groups at UCL Ear Institute (detailed explanation of these tests is given later):

- Baseline (before recruitment, 0 months into the study):
 - Pure Audiometry Test (PTA)
 - Non-verbal IQ test (Wechsler test of Non-verbal intelligence)
 - Children Questionnaires (LIFE-R)
 - Attention test (TEACH)
 - Listening in Spatialised noise (LiSN-S)
 - Questionnaires (CHAPS, CCC-2)
- At 3 months

- Children Questionnaires (LIFE-R)
- Attention test (TEACH)
- Listening in Spatialised noise (LiSN-S)
- Questionnaires (CHAPS, CCC-2)
- At the end of the study (6 months later):
 - Children Questionnaires (LIFE-R)
 - Attention test (TEACH)
 - Listening in Spatialised noise (LiSN-S)
 - Questionnaires (CHAPS, CCC-2)

Explanation of each test:

1. A hearing test (Pure Tone Audiometry approx. 10mins). To determine their hearing is normal.
2. Non-verbal IQ test (Weschler test of non-verbal intelligence). To be performed by the PhD Student. (approx. 15mins). To assess determine whether their intelligence level is above normal.
3. Listening in spatialised noise test (LiSN-S, approx. 15mins). To be administered through the use of headphones by the PhD student. To determine their listening in spatialised speech noise abilities.
4. An attention test. The Test of Everyday Attention for Children (TEACH). To be conducted as play type activities by the PhD student after receiving sufficient training by the clinical psychologist. (approx. 45mins possibly cut down to 30mins). To assess their attention.
5. Two questionnaires to be filled by the children's parents.
 - a. The Children's Communication Checklist-2 (CCC-2). A 70-item questionnaire which screens for communication problems (including language disorders and autism).
 - b. The Children's Auditory Performance Scale (CHAPS). It assesses aspects of children's listening.
6. One questionnaire to be completed by the children (Listening Inventory For Education-Revised [LIFE-R] for assessing their listening difficulty.

Data analysis:

Data were analysed in SPSS 22 statistics software, using a mixed ANOVA, with group as the between-subjects factor with two levels (i.e. control or RMHA) and time the within-subjects factor with three levels (i.e. baseline, 3, and 6 months) .

Other issues:

None of these tests are invasive or unpleasant, and they are conducted in comfortable sound levels (slightly higher than the usual conversational level). Any additional information on the children that might emerge during the study will be reported back to the clinician at the APD clinic to inform the child's management.

All children who participate will receive a book voucher of £10 at the end of each test session. Travel expenses will also be reimbursed (up to £10).

References

3. American Speech-Language-Hearing Association. (Central) Auditory Processing Disorders. Technical Report [Internet]. American Speech-Language-Hearing Association. 2005 [cited 2019 Aug 6]. Available from: <http://www.asha.org/policy/TR2005-00043/>
4. American Academy of Audiology. American Academy of Audiology Clinical Practice Guidelines. Diagnosis, Treatment and Management of Children and Adults with Central Auditory Processing Disorder [Internet]. American Academy of Audiology. 2010 [cited 2019 Aug 6]. p. 1–51. Available from: <http://www.audiology.org/publications-resources/document-library/central-auditory-processing-disorder>

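### Hypothesis ii predicts no greater improvement with RMHAs, but the only planned analysis is a difference test, so the plan cannot separate no benefit from an inconclusive result

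*Combined protocol and SAP*

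**What the plan says.** Hypothesis ii, under Aim and hypotheses, states: "Children with APD who use the RMHA will not show greater improvements in listening in spatialised speech noise and divided and visual attention measures", judged at 6 months with the control group as comparator. The Summary puts it more broadly: "we hypothesise that listening in spatialised noise and attention skills will remain unchanged following the intervention period".

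Hypothesis i points the other way for one attention measure: "Children with APD who use RMHAs will show greater improvements in classroom listening, listening in noise and sustained auditory attention (unaided) after 6 months".

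Under Participants and Recruitment, the sample size is "based on an estimated 0.5 effect size" f(U), with 80% power, 5% significance, two groups and three measurement points, for the between-within interaction. This gives 24 children, raised to 26 for 10% loss.

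Data analysis describes one method: "Data were analysed in SPSS 22 statistics software, using a mixed ANOVA, with group as the between-subjects factor with two levels", and time (baseline, 3 and 6 months) as the within-subjects factor. No section gives a margin, a confidence-interval rule or any other criterion for judging hypothesis ii.

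The principal question appears twice. The Summary has "The principal research question is whether RMHAs improve classroom listening, listening in noise performance, listening in spatialised noise and auditory attention". Aim and hypotheses has "The principal research question was to examine the effects of RMHAs on classroom listening, listening in noise performance, and auditory attention", without spatialised noise.

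**The concern.** A difference test can contradict a prediction of no greater improvement. It can support the prediction only if controls improve significantly more. In every other case the candidate evidence is a non-significant interaction, which arises both when there is no benefit and when there is a benefit that the trial is too small to see. The plan gives the report no means of telling these apart.

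At stake are three outcome domains: spatialised noise, divided attention and visual attention. A conclusion that the device leaves them unchanged could be drawn from a result that is compatible with a worthwhile gain.

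The attention predictions raise a separate problem. The Summary makes a blanket prediction of no change in attention skills, while hypothesis i predicts a gain in sustained auditory attention. As written, either result on that measure could be reported as confirming a stated hypothesis.

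**Working it through.** **1. The plan's own figure.** Inputs from Participants and Recruitment: f(U)=0.5, alpha 0.05, k=2 groups, m=3 times. For the interaction, df1=(k−1)(m−1)=2, df2=(N−k)(m−1) and λ=f(U)²(N−k)(m−1), with sphericity assumed.

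- N=22: df2=40, λ=0.25×20×2=10.0, power 78.4%.
- N=24: df2=44, λ=0.25×22×2=11.0, power 82.6%.

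So 24 is the smallest even total that reaches 80%. The stated size reproduces and is not disputed.

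**2. What the same test misses.** This step keeps the plan's scale and assumes no correlation.

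- N=24, f(U)=0.25: λ=0.0625×44=2.75, power 28.0%, missed in 72%.
- N=26, f(U)=0.25: λ=0.0625×48=3.00, power 30.4%, missed in 70%.
- N=24, other sizes: missed in 17% at f(U)=0.5, 37% at 0.4, 61% at 0.3 and 81% at 0.2.

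A non-significant interaction is therefore the expected result for an effect half the size planned for.

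**3. Outcome-SD scale.** These inputs are assumptions, because the documents do not give them: 1:1 allocation, a constant within-child correlation ρ, a reference effect of 0.5 SD, and the pattern of the effect over time.

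*Miss rate.* λ=(n/2)Σ(d_t−d̄)²/(1−ρ), with df (2, 4n−4). For n=12 per arm, ρ=0.5 and group differences of 0, 0.25 and 0.5 SD at the three visits, Σ=0.125 and λ=6×0.125/0.5=1.5, so the effect is missed in 83%. The table gives the range over 12 to 13 per arm and two patterns (0, 0.25, 0.5 and 0, 0.5, 0.5).

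*Baseline-adjusted 95% CI half-width, 12 per arm.* t(21)×√(2(1−ρ²)/12), with t(21)=2.080. At ρ=0.5 this is 2.080×√(1.5/12)=2.080×0.354=0.74 SD.

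*Chance of excluding 0.5 SD when the true difference is zero.* This is the probability that the upper limit falls below 0.5 SD, from the noncentral t distribution with 21 df and noncentrality 0.5/SE, at two error levels.

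| ρ | True 0.5 SD missed by interaction test | Adjusted 95% CI half-width | Excludes 0.5 SD, one-sided 2.5% | Excludes 0.5 SD, one-sided 5% |
|---|---|---|---|---|
| 0.5 | 77–83% | 0.74 SD | 27% | 39% |
| 0.7 | 64–74% | 0.61 SD | 37% | 51% |
| 0.8 | 49–63% | 0.51 SD | 50% | 63% |
| 0.9 | 18–34% | 0.37 SD | 76% | 86% |

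If the group difference in change is used instead, the half-width is t(22)×√(4(1−ρ)/12), with t(22)=2.074: 0.85, 0.66, 0.54 and 0.38 SD.

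**4. The attention predictions side by side.**

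| Measure | Summary | Aim and hypotheses |
|---|---|---|
| Sustained auditory attention | no change (all attention skills) | greater improvement (hypothesis i) |
| Divided and visual attention | no change | no greater improvement (hypothesis ii) |

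Only the first row is a direct contradiction. The second differs in form: the Summary reads as no change over time, and hypothesis ii as a one-directional comparison with controls.

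**The case against.** The strongest reply is that hypothesis ii is only an expectation. The documents nowhere promise to demonstrate equivalence, and nowhere say that p>0.05 will count as support. A reader might infer that they do, but the text does not support that. What stands against the reply is that hypothesis ii is a formal, numbered prediction with no criterion, so the report still needs a rule for a null result.

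Second, hypothesis ii is one-directional, so a significant interaction favouring controls would support it. That is correct, and it is why the point is limited to the remaining cases.

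Third, the SD-scale results depend on choices that the documents do not make. This also stands. At ρ=0.7 the chance of excluding 0.5 SD is 37% or 51% depending on the error level, and at ρ=0.9 a null result would usually exclude it. A reader might infer that this trial could never rule out a moderate benefit, but the figures do not show that. The plan-scale figure of 72% needs no correlation.

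Fourth, a reader might see a serious conflict in whether the principal question lists spatialised noise. The aim stated just above the second version of that question already covers this domain, and no analysis, alpha or sample size depends on the label. It is a minor wording point.

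**Conclusion.** The concern holds, and should be fixed. The stated analysis does not fit hypothesis ii: unless controls improve significantly more, nothing it can produce separates no benefit from inconclusive. On the plan's own scale, a true interaction of half the planned size is missed in 72% of trials at N=24 and 70% at N=26, assuming sphericity. The SD-scale figures rest on assumed correlation, margin, error level, time pattern and equal allocation, and should be read as a range.

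It does not follow that the sample size is wrong. The 24 is correct for the difference test it was computed for; it simply does not address hypothesis ii.

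The contradiction over sustained auditory attention is real but is a matter of wording, and it adds nothing to the severity of the analysis point.

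**What to change.** For each hypothesis ii outcome, scored so that positive values favour the device, report the baseline-adjusted 6-month group difference with its 95% CI. If the mixed-ANOVA framework is kept, report the group difference in change with its interval instead. State that p>0.05 is not support for no benefit. Report the result as inconclusive unless the interval excludes a margin that was justified before the data were seen. Data analysis is written in the past tense, so it may be too late for such a margin. Any margin set later should be labelled post hoc and used descriptively only.

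In the same revision, reconcile the Summary with hypotheses i and ii so that sustained auditory, divided and visual attention each carry one stated prediction, and use one wording of the principal question throughout.

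The cost is small: no new data or visits, one interval per outcome, one interpretation rule and a few reconciled sentences. The downside is that conclusions of no change become weaker, and several may have to be reported as inconclusive unless the within-child correlation is high.

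### Deleting every withdrawn child's data leaves a completers-only comparison, whose possible bias could then be neither corrected nor checked

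*Combined protocol and SAP*

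**What the plan says.** The rule is in the Data protection section: "If withdrawals take place the participants' data will be deleted". The protocol text does not limit it by time point, arm, reason or parental request. The section on rights to withdraw adds that "participants will be allowed to withdraw from the study at any point should they wish to do so", so a child can leave after allocation and after one or two test sessions.

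Under Intervention ethical issues, the no-intervention control group is promised the device later: "this group will receive the RMHA after we complete the study, at 6 months".

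Participants and Recruitment derives a total of 24 and then allows for attrition: "To account for a 10% loss due to follow-up, the total sample size of this study was 26 children". It gives no expected number of withdrawals by arm.

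The Data analysis section gives one method, "using a mixed ANOVA, with group as the between-subjects factor with two levels", with baseline, 3 months and 6 months as the within-subject factor. The documents name no analysis set, missing-data method, sensitivity analysis or reporting of withdrawals by arm.

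**The concern.** Two features act together. The deletion rule removes all of a withdrawn child's scores. A repeated-measures ANOVA in its standard form also drops any child missing one visit; this is a property of the method, since the plan is silent. What remains is a comparison of completers.

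That is harmless if leaving has nothing to do with response, or if it acts equally in both arms. Neither can be assumed here. RMHA families already have the device and must fit it into the school day, while control families are waiting for it. The reasons to stay differ by arm, and the direction of any imbalance is unknown.

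If leaving is both related to response and different by arm, the groups analysed are no longer the groups allocated, and the comparison of change is biased towards or away from the device. With deletion, the data that would show whether this had happened no longer exist.

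**Working it through.** **1. The plan's own figure.** Inputs from Participants and Recruitment: f(U) = 0.5, 80% power, 5% significance, k = 2 groups, m = 3 measurements. For the within-between interaction under sphericity, λ = f(U)²(N − k)(m − 1), df1 = (k − 1)(m − 1), df2 = (N − k)(m − 1).

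- N = 24: λ = 0.25 × 22 × 2 = 11, df = 2 and 44, power 0.826. The smallest N reaching 80% is 23, or 24 with equal arms, so 24 reproduces.
- Recruiting 26 with 10% loss leaves 26 × 0.9 = 23.4; power at 23 is 0.806.

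Power therefore survives the planned loss. The problem is bias.

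**2. How many children.** 10% of 26 is 2.6. This is overall loss to follow-up, not a count of deleted withdrawals, so two or three is an illustrative number.

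**3. Assumptions not in the documents.** 13 per arm (the ratio is not stated), no true effect, unit SD at each visit, compound symmetry with correlation ρ of 0.5 or 0.7, and losses after month 3.

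**4. Expected bias when the worst 3-month changes leave.** The SD of a change score is √(2(1 − ρ)): 1.00 at ρ = 0.5 and 0.775 at ρ = 0.7. The covariance of the 3-month and 6-month changes is 1 − ρ and each has variance 2(1 − ρ), so their correlation is 0.5. Removing the lowest two of 13 raises the mean of the rest by 0.257 SD of the selected variable; removing three raises it by 0.367 SD.

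- Two leave: 0.257 × 0.5 × 1.00 = 0.13; 0.257 × 0.5 × 0.775 = 0.10.
- Three leave: 0.367 × 0.5 × 1.00 = 0.18; 0.367 × 0.5 × 0.775 = 0.14.

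**5. Simulation of the completers' mixed ANOVA** (40,000 trials per case; each pair is ρ = 0.5, ρ = 0.7). Bias is in the between-arm difference in 6-month change; rejection is of the nominal 5% interaction test.

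| Who leaves | Bias (SD) | Rejection |
|---|---|---|
| Nobody | 0.00, 0.00 | 0.050, 0.048 |
| Two or three at random | 0.00 | 0.048 to 0.051 |
| Worst one from each arm | 0.00, 0.00 | 0.062, 0.064 |
| Two worst RMHA | +0.126, +0.100 | 0.089, 0.090 |
| Three worst RMHA | +0.184, +0.143 | 0.123, 0.119 |
| Two RMHA, weaker link | +0.077, +0.057 | 0.062, 0.063 |
| Three RMHA, weaker link | +0.108, +0.087 | 0.073, 0.072 |
| Two worst controls | −0.127, −0.098 | 0.088, 0.087 |

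The weaker link gives each child a leaving weight of exp(−z), with z the standardised 3-month change. The simulated biases match step 4.

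With three worst RMHA leavers, the SD of the estimate is 0.418 or 0.323, so the bias is 0.184/0.418 = 0.143/0.323 = 0.44 of a standard error. The raw 6-month difference, without subtracting baseline, is unbiased in all these cases: the covariance of the 6-month score with the 3-month change is ρ − ρ = 0.

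**6. What keeping the data gains.** A REML mixed model using the retained baseline and 3-month scores (2,000 trials per case) has bias between −0.009 and +0.010 and rejection of 0.044 to 0.061 when leaving depends on the 3-month change.

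**7. What it does not gain.** If leaving depends on the unseen 6-month change, completer bias is 0.261, 0.202 (two leave) and 0.366, 0.285 (three). The mixed model still leaves 0.158, 0.135 and 0.249, 0.200, which is 61% to 70% of it. Shifting the missing scores by 1 SD moves the arm mean by 2/13 = 0.15 or 3/13 = 0.23 SD, close to what remains. That is the reason for the sensitivity range proposed below.

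**The case against.** The strongest objection is about cause. A child lost after month 3 would be dropped by the planned ANOVA whether or not the data were deleted, so the biases in the table belong to complete-case analysis, not to the deletion sentence alone. This is right as far as it goes. Deletion adds something different: it rules out the analysis in step 6 that would remove the bias, and any comparison of leavers with stayers.

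The 9% and 12% rates also overstate the problem for the 6-month question. They belong to the planned interaction test, which uses all three visits. A test of 6-month change alone rejects about 6% (two leave) to just under 8% (three leave). The excess comes mainly from the 3-month contrast, on which the leavers were selected. That stands, and the rates should be read as those of the planned test only.

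The mechanism is conjectural. Nothing in the documents says poor responders leave. Families are told that leaving carries no penalty, and vouchers and travel refunds encourage attendance in both arms. A child who stops using the device but still attends is not covered by the rule. This limits how likely the worst cases are, but does not remove the exposure.

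Deletion can also be a defensible privacy commitment, and the consent form, which was not available here, may qualify it. The protocol text, however, makes deletion automatic and not dependent on a request. Counts by arm could survive deletion and allow crude bounds, but the plan does not provide for them. Finally, the document is dated 26/03/20 and describes the analysis in the past tense, so new consent wording may come too late. That affects which part of the fix applies, not the point itself.

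**Conclusion.** The concern holds and should be fixed. Followed as written, the deletion rule and the three-visit ANOVA can yield only a completers' comparison. Bias arises only if leaving is both related to response and different by arm; with random loss, or the worst child lost from each arm, there is none.

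In the main one-arm cases the bias in 6-month change is 0.06 to 0.18 SD in size, at most about 0.44 of a standard error, with interaction-test rejection of 6% to 12%. If leaving tracks the unseen 6-month change, the bias reaches 0.20 to 0.37 SD. These figures rest on 13 per arm, compound symmetry, correlations of 0.5 to 0.7 and two or three losses after month 3, none of which the documents fix. Confidence is medium, because the true number and pattern of withdrawals are unknown.

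**What to change.** 1. Replace the deletion sentence with: *Coded data collected before withdrawal are kept and analysed in the arm assigned, unless the parent asks for deletion.* Use the same wording in the information sheet and consent form, and honour any deletion promise already made.
2. Replace the mixed ANOVA with a linear mixed model fitted by REML, using every available visit from every allocated child.
3. Report the number and timing of withdrawals, and of deletions, by arm.
4. Add a sensitivity analysis, because the model removes the bias only when leaving depends on scores already observed. Lower the missing 6-month scores in the RMHA arm by 0.5 and 1.0 baseline SD, repeat for the control arm, and state whether the conclusion changes.
5. If data have already been deleted, label the result a completers-only analysis.

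The cost is a wording amendment, a different model and one short sensitivity analysis, with no extra visits or staff. Parents who ask for deletion still get it, so some data may remain missing.
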